## **4. SUBJECT POPULATION**

### **4.1. Number of Subjects and Subject Selection**

At least 300 subjects will be enrolled in this study (150 at each site).

### **4.2. Inclusion Criteria**

Subjects must meet *all* of the following inclusion criteria to be eligible for participation in this study.

- (1) Age 18-65 years;
- (2) Self-reported use of non-prescribed opioids in past 14 days;
- (3) Current moderate-to-severe opioid use disorder by DSM-5;
- (4) Urine positive for opioids by point-of-care testing during screening (or self-reported illicit opioid use in the past 4 days, confirmed by a trusted source, for remote or other visits in which urine cannot be collected)
- (5) History of prior opioid overdose within past 3 years;
- (6) Previously received take-home naloxone;
- (7) No life-threatening illnesses likely to progress clinically during trial;
- (8) Able and willing to provide informed consent, provide adequate locator information, communicate in English, adhere to visit schedule.

### **4.3. Exclusion Criteria**

Subjects who meet *any* of the following exclusion criteria are not to be enrolled in this study.

- (1) Suicide plan or attempt within 12 months prior to screening;
- (2) Urine positive only for prescribed agonist maintenance therapy and negative for cocaine and methamphetamine (if urine cannot be collected precautions, this criterion will not apply);
- (3) Currently participating in another interventional research study that could possibly impact the study's outcomes of interest;
- (4) Planning to leave San Francisco/Boston metro area during study;
- (5) Previously exposed to REBOOT counseling intervention;

- (6) Any condition that, in the Principal Investigator's judgment, interferes with safe study participation or adherence to study procedures.

## 5. STUDY PROCEDURES

The study procedures to be conducted for each subject enrolled in the study are presented in tabular form in **Error! Reference source not found.1** and described in the text that follows.

The investigator will document any deviation from protocol procedures and notify appropriate regulatory authorities (e.g., IRB and/or NIH).

### 5.1. Subject Enrollment and Treatment Assignment

Active recruitment will occur at a variety of community locations including, but not limited to, syringe access sites, naloxone distribution sites, the Boston Public Health Commission Engagement Center (Boston site only), local community-based organizations, and SUD treatment centers. Additionally, we will utilize passive recruitment methods through distribution of recruitment materials such as posters, cards, and flyers which will be left at places frequented by opioid users. We will also recruit participants via snowball sampling. Any enrolled REBOOT participant (who was consented, screened, and completed the baseline visit) may refer individuals to the study. Participants will be compensated \$40 per person who they refer who is eligible and enrolls in the study (for a total of up to 5 people or \$200). Participants will be informed of the snowball sampling process during study visits.

Individuals who express interest will complete a brief prescreening questionnaire administered by staff either over the phone or in person. Those deemed eligible per the prescreener will then be scheduled for a screening visit where informed consent will be signed, or verbal consent will be given (for remote or other visits in which urine cannot be collected), and final eligibility will be determined. Eligible participants will be scheduled for an enrollment visit at which time they will complete the baseline assessment and be randomized to either the counseling intervention or the attention control group, as described below. Follow-up visits will occur every four months for 16 months and will be completed primarily in person, but may also be completed over the phone if necessary.

### 5.2. Pretreatment Assessments

N/A

### 5.3. Screening Visit

Participants will be prescreened by trained research staff using IRB-approved procedures. Staff will inform participants of the study, emphasize that participation is voluntary, and provide them with IRB-approved flyers that describe the study. Research staff will administer the prescreening questionnaire to interested participants either over the phone or in person. Those who remain eligible will complete an in-person or remote screening visit. Participants will be informed before the visit that they may still be found ineligible for the study but that they will be compensated for their time.

Informed consent will be obtained at the beginning of the screening visit. After consent is obtained and eligibility is determined, a locator form is completed and HIPAA and release of information forms are signed for review of medical/criminal records. In the case of remote screening visits, verbal consent will be obtained for the informed consent and HIPAA, and the release of information will be omitted. The screening visit will also include Structured Clinical Interview for DSM-5 for opioid use disorder and assessment for suicidal ideation, as well as a urine drug screen with expanded opioids and fentanyl.

Subjects meeting all of the inclusion criteria and none of the exclusion criteria will return to the study site within 28 days after screening for enrollment into the study; enrollment may occur remotely if absolutely necessary due to COVID-19 precautions. Subjects who do not complete enrollment within 28 days may be considered for rescreening on a case-by-case basis, dependent upon the reason for non-enrollment.

Participants will be compensated \$20 for the screening visit. Participants will not be compensated for completing the prescreener.

### **5.3.1. Enrollment Visit**

Enrollment procedures will be completed prior to randomization and receipt of the first counseling or attention control session.

For in-person enrollment visits, participants will provide a urine sample for toxicology testing and research staff will administer the baseline assessment. Participants will update the locator form and have their picture taken to store with their locator form (this may also be done at screening if deemed appropriate). In the event of a remote enrollment visit, urine sample and photo will not be collected.

After completing the baseline assessment, participants will be randomized to receive either the behavioral intervention (n=150) or attention control (n=150). **Randomization** will be 1:1 using permuted blocks of randomly selected sizes. Randomization will be followed by initial counseling for the treatment group and attention control for the reference group. The next visit will be scheduled and participants will be compensated for their time.

Participants will be compensated \$50 for the enrollment visit.

### **5.3.2. Interim Contact**

Study staff will attempt to contact participants at two-month intervals between scheduled study visits (i.e. months 2, 6, 10, and 14) in order to update locator forms. This contact may be made by phone, other electronic means, or in person. Participants will be compensated \$3 for updating contact information, either at the time of updating or at their next in-person visit.

Staff may attempt more frequent contact with participants at-risk to being lost-to-follow-up, however participants will not be compensated for these additional contacts.

#### **5.4. Follow-up Visits (Month 4, 8, 12 and 16)**

Participants will complete follow-up assessments every 4 months.

At months 4, 8 and 12, participants will provide a urine drug screen (for in-person visits only), complete the assessment, update their locator form, and receive counseling for the treatment group or attention control for the reference group.

At month 16, participants will provide a urine drug screen (for in-person visits only) and complete the assessment. REBOOT participants will not receive counseling at month 16, and attention control participants will not watch a video nor listen to a podcast at month 16. Participants will not update their locator forms at month 16.

If participants are in a facility at the time of the follow-up visit (i.e. hospital, substance use disorder treatment facility), every effort will be made to reach that participant to complete visit activities. These activities may be completed at the facility if feasible to staff and approved by the facility. Alternatively, assessments may be completed in-person or over the phone if intervention/control sessions are not feasible.

Subjects who have a phone will be compensated as follows: \$60 for month 4 visit, \$70 for month 8, \$80 for month 12, and \$100 for month 16. Payments are in the forms of cash or gift card.

As a retention strategy, participants who are not reliably reachable will be required to accept a study cell phone with unlimited minutes in lieu of the cash or gift card stipend. Participants will be informed of this requirement during the informed consent process. If at any visit a participant has their own phone, they will not be required to accept a study cell phone as payment.

#### **5.5. Reliability Substudy Visit**

REBOOT participants that complete the Month 16 visit may be invited to participate in one additional brief assessment (Timeline Follow Back re-test). Consent for this substudy visit will be obtained separately. In this visit, the participant will be administered the portion of the assessment for a time period already assessed during the study. The purpose of this re-test is to assess the reliability of the data captured in the assessment. We aim to re-test up to 100 participants. Participants will be compensated \$50 for the additional visit.

#### **5.6. Assessments**

##### **5.6.1. Labs**

Urine drug screen (drugs of abuse screen/expanded opioids) will be done at all in-person visits.

##### **5.6.2. Research Electronic Data Capture (REDCap)**

Research staff will verbally administer assessments to participants using REDCap at enrollment and months 4, 8, 12, and 16. Assessments may be completed on paper and later entered into REDCap (e.g. if research staff are not permitted to bring electronic devices when conducting

interviews in a jail). The assessment will **always** be conducted by a staff person blinded to the participant's study arm and prior to administration of the REBOOT intervention or control arm procedures.

The assessment, which is administered at enrollment and months 4, 8, 12, and 16 includes items related to demographics (enrollment only), drug use history (enrollment only), opiate overdose, drug use, treatment, drug-related risk behaviors, incarceration, hopelessness, impulsivity, participant satisfaction with treatment, and questions related to COVID-19 and its impact on various aspects of participants' lives. As part of the assessment, we will record participants' COVID-19 vaccination status.

Primary and secondary outcome variables will be obtained from standardized scales or established approaches. We will utilize overdose measures developed in collaboration with other investigators (Drs [name], [name], [name], and [name]) to maximize comparability among overdose studies.

The following standardized scales will be administered and included in the assessment, regardless of study arm:

- **Severity of Dependence Scale:** This 5-item questionnaire measures severity of dependence on opioids (Gossop et al., 1995). It will be administered at all study visits.
- **Abbreviated Impulsiveness Scale (ABIS):** Derived from the Barratt Impulsiveness Scale version 11 (BIS-11), the ABIS is a 13-item measure of trait impulsivity (Coutlee et al., 2015). This scale will be administered at enrollment and month 16.
- **Brief-Neg-H & Brief-Pos-H:** This brief (4-item) measure of hopelessness contains two negatively-worded items and two positively-worded items, and has demonstrated concurrent validity with the Beck Hopelessness Scale (BHS) and the Center for Epidemiologic Studies Depression (CES-D) scale (Fraser, et al., 2014). It will be administered at all visits.
- **Addiction Severity Index (ASI):** We will administer an adapted version of the ASI Drug Use Module at each study visit (McClellan et al., 1980).

### 5.6.3. Administrative data

If research staff learn that a participant has died during their participation in the study, date and cause of death will be ascertained from **Vital Records**, as well as from contacts listed on locator forms. Deaths will be reported as SAEs in accordance with IRB and GCP procedures.

Data from local emergency departments and hospitals may be obtained on some or all participants through signed ROIs during enrollment in order to assess for opioid overdose-related visits, as a means of validating self-report data.

#### **5.6.4. Data Management**

Data will be maintained in REDCap (tracking, administrative, and survey data). REDCap is more secure than Microsoft Excel or Access and can be accessed from any device with an internet connection and web browser. It is HIPAA-compliant, offers daily backups, and has an audit trail for increased security. Any paper forms will be stored with participant files in locked offices, separate from identifying information per GCP guidelines.

## 6. ADVERSE EVENTS MANAGEMENT

### 6.1. Definition of Adverse Events and Serious Adverse Events

Participants will be queried as to adverse events at the beginning of each visit. We will use the DAIDS Table for Grading the Severity of Adult and Pediatric Adverse Events Corrected Version 2.1, July 2017, available at: <http://rsc.tech-res.com/safetyandpharmacovigilance/>

We will record and report all AEs in accordance with these NIH guidelines. Safety monitoring will include the assessment, follow-up, and reporting of clinical AEs and serious AEs (SAEs). Each AE will be classified by the study clinician/principal investigator as serious or non-serious, and appropriate reporting procedures will be followed.

All AEs that are serious and meet the reporting criteria will be reported to NIDA and the DSMB within 72 business hours of learning of the SAE and to the UCSF IRB within 5 working days if they meet IRB reporting requirements. UCSF IRB is the primary IRB for both study sites.

A Serious Adverse Event (SAE) will be defined according to the guidelines set forth by the FDA (<http://www.fda.gov/safety/medwatch/howtoreport/ucm053087.htm>) with the modification for the primary outcome of overdose.

A *serious AE* is any untoward medical occurrence:

- results in death,
- is life-threatening (defined as an event in which the patient was at risk of death at the time of the event; it does not refer to an event which hypothetically might have caused death if it were more severe),
- requires inpatient hospitalization or causes prolongation of existing hospitalization,
- results in persistent or significant disability/incapacity,
- is a congenital anomaly/birth defect,
- is an important medical event (defined as a medical event(s) that may not be immediately life-threatening or result in death or hospitalization but, based upon appropriate medical and scientific judgment, may jeopardize the patient or may require intervention (e.g., medical, surgical) to prevent one of the other serious outcomes listed in the definition above).

Overdose events will be reported as SAEs if they result in hospitalization or death. Follow-up information which becomes available as the SAE evolves, as well as supporting documentation (e.g., hospital discharge summaries and autopsy reports), will be collected subsequent to reporting, if not available at the time of the initial report, and immediately sent using the same procedure as the initial SAE report.

SAE reporting will include a narrative that will provide details of relevant screening measures, medical history and physical, treatment compliance, participant reports of SAEs, and any other required information. The completed SAE form will contain the participant's ID#, gender, and age; the title and date of the SAE; and narrative explanation. The SAE form will track how the research staff was notified of the event; dates of consent, randomization, and study screening for inclusion/exclusion; study treatment received (visits attended, as staff will be blinded to

treatment arm); other relevant clinical information; dates and circumstances of the hospitalization/death; whether alcohol or drugs were known to be involved; and participant status at last clinical or research contact. The investigators will state whether the event was expected and assess its relatedness to the study intervention. A summary report of all AEs (including SAEs) will be submitted to the DSMB in the annual progress report.

For more information on protocol for AEs and SAEs, please refer to the DSMP protocol.

## **6.2. Management of SAEs and other study risks**

We do not anticipate significant risks to the safety of participants due to study participation. An interim analysis will be conducted as described in section 7.1 of the DSMP to ensure that the study is not continued as designed if there is clear benefit or harm to the intervention or if there is no hope of demonstrating an effect of the intervention; this will be determined by analyzing the frequency of overdose events.

Should participants require acute medical care during study participation, they will be treated on-site by a clinician if available and, once stabilized, taken to the appropriate hospital for care; if a clinician is not available, emergency medical assistance will be sought and the participant transported to the appropriate hospital.

In the case of remote visits, staff will be able to reach the clinical psychologist, nurse practitioner or medical doctor by phone or text, if needed. At the beginning of remote visit calls, participants will be asked for their current location so that staff may provide that information to a 911 operator, if necessary.

## **6.3. Reporting of SAEs**

All AEs that are serious and meet the reporting criteria will be reported to NIDA and the DSMB within 72 business hours of learning of the SAE and to the UCSF IRB within 5 working days if they meet IRB reporting requirements. UCSF IRB is the primary IRB for both study sites.

A Serious Adverse Event (SAE) will be defined according to the guidelines set forth by the FDA (<http://www.fda.gov/safety/medwatch/howtoreport/ucm053087.htm>) with the modification described in 6.2 of the DSMP for the primary outcome of overdose.

An expedited reporting of SAE will adhere to the following guidelines:

- a) Apply regardless of the investigator's assessment of the relatedness of the SAE to the intervention under study.
- b) Apply equally to trials requiring an IND and those not requiring an IND.
- c) Apply to any SAE that occurs during the post-treatment observation period defined by the protocol.
- d) Apply to suicidal or homicidal behavior that causes an SAE in the subject or someone else (e.g. hospitalization or death).

## 7. CHANGES TO STUDY PROTOCOL

### 7.1. Reporting of IRB actions and DSMB reports to NIDA

Through the study project officer, NIDA will be informed of IRB actions regarding the study and provided the annual DSMB report. When significant revisions to the protocol are planned, IRB and DSMB communications will be forwarded to the NIDA Project Officer (PO), [name], [contact], email: [[contact]](mailto:[contact]).

### 7.2. Report of changes or amendments to the protocol

All changes and amendments to the study protocol will require IRB approval prior to their implementation. When appropriate, the NIDA project officer will be informed of changes or amendments to the study protocol. Changes to the DSMP must also be approved by the DSMB and NIDA prior to implementation.

### 7.3. Trial stopping rules

Please see section 7.1 of the DSMP for details of interim analysis and stopping rules, including stopping for benefit, harm, or futility.

In addition, if it becomes clear that the trial puts undue safety risk on study participants or the trial will not achieve its enrollment goals, consideration will be given to stopping the trial, after consultation with the DSMB, IRB, and NIDA PO.

The overall safety risk to study participants will be determined through regular monitoring procedures. Study staff will consult with Drs. [name] and/or [name] on these safety issues on a case-by-case basis as they are reported by participants. Non-urgent clinical issues that arise during the course of the study are discussed by the research staff at the next weekly meeting with Drs. [name] or [name]. During weekly meetings, study staff will review all safety issues and incident adverse events for the study overall, by system category, and by possible relationship to the behavioral intervention. The PI will alert the DMSB and the NIDA P.O. immediately if at any point the team observes an unexpected frequency of serious AEs possibly related to the intervention. Of note, to maintain the partial blind, only interventionists will know the study arm of each participant.

### 7.4. Disclosure of conflicts of interest

Staff are required to disclose any financial conflicts of interest with the study. Signed documentation of conflicts of interest (or lack thereof) by study investigators will be provided to the IRB as required by the initial and continuing review process.

## **8. STATISTICAL CONSIDERATIONS**

### **8.1. Analysis Objectives**

#### **8.1.1. Analysis Objectives**

The primary objectives of this study are:

1. To adapt REBOOT intervention to ensure relevance in a setting heavily affected by fentanyl using the ADAPT-ITT process.
2. To determine if REBOOT, compared to attention control, reduces during 16 months of follow-up
  - a. the number of opioid overdose events, or
  - b. the occurrence of any opioid overdose
3. To determine if REBOOT, compared to attention control increases
  - a. the number of days abstinent from opioid use, or
  - b. days in substance use treatment.

The exploratory objectives of this study are:

- 1) To determine the efficacy of REBOOT first by site, then in affecting several secondary outcomes, such as modifiable risk behaviors and management of witnessed overdose.

### **8.2. Analysis Conventions**

All individual subject data will be listed as measured. All statistical summaries and analyses will be performed using STATA® software.

### **8.3. Demographic Data and Baseline Characteristics**

Demographic and baseline characteristics will be summarized using standard descriptive methods by treatment group and overall.

Demographic data will include sex, self-identified race/ethnicity, and age.

### **8.4. Data Analysis**

#### **8.4.1. Primary Analysis**

- 1) Specific Aim 1: We will utilize ADAPT-ITT to ensure REBOOT's relevance in the context of fentanyl. We will produce a manuscript describing the process and outcomes, similar to that which we produced for a prior adaptation study of Personalized Cognitive Counseling that was accepted as a CDC Evidence-Based Intervention (<https://tinyurl.com/ybx3oqep>). While the manuscript will describe the process and outcomes from each ADAPT-ITT Phase, a major element of this analysis will be the theater test and focus group (Phase 3). Sessions will be audio-recorded and transcribed verbatim. Two independent analysts will develop a codebook and independently code the focus group transcript. The transcript will then be analyzed using standard thematic content analysis. The topical expert review (Phase 6) will also be a key element in

describing the adaptation process, as well as the final product of the adapted intervention manual.

- 2) **Specific Aim 2a:** Number of overdose events occurring during follow-up
  - a. To determine if REBOOT, compared to attention control, reduces the occurrence of any opioid overdose event, we will use generalized estimating equations (GEE) models for the occurrence of any OD event in each reporting period, with robust standard errors to account for within-subject correlation of the repeated measures.
- 3) **Specific Aim 2b:** Occurrence of any opioid overdose event during follow-up
  - a. To determine if REBOOT, compared to attention control, reduces the number of opioid overdose events, we will use GEE Poisson models for the number of OD events in each reporting period, set up in the same way as the model for Aim 2a.
- 4) **Specific Aim 3:** Number of days not using opioids and number of days engaged in treatment for opioid use disorder during follow-up
  - a. To determine if REBOOT, compared to attention control, increases the number of days abstinent from opioid use and days in substance use treatment, we will use GEE Poisson models for each of these outcomes, both set up in the same way as the models for Aims 1 and 2.

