GEE Poisson models for the number of overdose events in each reporting period, set up in the same way as the model for Aim 1. In this case, robust standard errors will be needed to account for within-subject correlation and potential over-dispersion (rather than under-dispersion) of the count outcome. We expect that repeated overdose events may be reasonably common in a subset of higher risk participants. The sensitivity analyses proposed for Aim 1 will be repeated for this outcome.

**Specific Aim 3:** To determine if REBOOT, compared to attention control, increases the number of days abstinent from opioid use or days in substance use treatment, we will use GEE Poisson models for each of these outcomes, both set up in the same way as the models for Aims 1 and 2. In addition, we will implement a Number-of-Beyond-threshold-Weeks-of-Success (NOBWOS) analysis, which will track by week the proportions of participants in each group who have achieved abstinence lasting through the end of the study.

**Sample size justification:** We estimate that the proposed sample of 300 participants, randomized 1:1 to REBOOT and attention control, will provide 80% power to detect net 59% reductions in the prevalence of any overdose by the final reporting period in the REBOOT group, conservatively accounting for net loss of 15% of participants by the end of the study. This is considerably smaller than the 83% net reduction observed in the pilot study. In making these calculations, we used data from the pilot to estimate baseline outcome rates by visit in the control condition, as well as the intra-class correlation of the repeated outcomes.

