## **Intervention Overview**

## Intervention Overview

### **10.3. Appendix 3. Descriptions and Dates of Amendments**

Amendment: 08/06/2020

1. Adjusted eligibility criterion regarding urine drug screen results. Because of COVID-19 precautions, one site may be in a new space that may not permit checking of urines. This amendment involves a "trusted source verification" protocol in which study staff contact professionals referred by the participant to confirm the participant's recent use of opioids. The process includes a detailed SOP for determining the result of the inquiry.
2. Clarified that eligibility criterion allowing potential participants currently treated with methadone or buprenorphine for opioid use disorder who report illicit opioid use but test negative for illicit opioids on urine drug screen to be enrolled if they test positive for cocaine or methamphetamine does not apply for eligibility assessments that do not include a urine drug screen.
3. Allow verbal consent and redcap consent collection in some situations due to COVID-19 precautions.
4. Added COVID-19 related questions and analyses, as well as remote versus in-person visit analysis plan, include adjustment to compensation for relevant visits.
5. Provide phone with plan in lieu of other compensation for visits when participant does not have personal phone.

Amendment: 12/28/2020

1. Increased screening payment from \$10 to \$20.

Amendment: 08/16/2021

1. Added snowball referrals from participants to recruitment methods. Active study participants will be compensated \$40 for up to five successful referrals to the study.
2. Added to procedures a one-time visit consisting of a brief assessment at the end of study participation. The purpose is to validate study activities in the assessment (specifically the time-line follow-back). Up to 40 participants will be compensated \$50 for this assessment. Consent for this visit will be obtained separately.
3. Specify that we will begin to collect COVID-19 vaccination status during the assessment at follow-up visits.

Amendment: 05/09/2023

1. Updated the number of participants who will be asked to participate in one-time visit consisting of a brief assessment at the end of study participation from 40 to 100.

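### Must the plan state how days on prescribed opioids, including agonist treatment, are scored in days abstinent (outcome 3a) and in the NOBWOS analysis?

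*Combined protocol and SAP*

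**What the plan says.** Aim 3 has two outcomes. The heading in section 8.4.1 calls them "Number of days not using opioids and number of days engaged in treatment for opioid use disorder during follow-up". The model sentence beneath it asks whether REBOOT "increases the number of days abstinent from opioid use and days in substance use treatment", and the objectives in section 8.1.1 likewise use "days in substance use treatment" for outcome 3b. Both outcomes get GEE Poisson models. The synopsis (Statistical Methods, Specific Aim 3) adds the NOBWOS analysis, which follows by week the proportion in each arm "who have achieved abstinence lasting through the end of the study".

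None of this text says how a day on a prescribed opioid is classified, and none cites an instrument for the day count. Section 5.6.2 says that outcome variables come from standard scales or accepted methods. It lists drug use and treatment among the survey topics and names an adapted ASI Drug Use Module at every visit, but ties none of these to outcome 3a.

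The closest text is in the counseling manual (Appendix 2). Under the review of definitions, the counselor tells the participant that the session uses the survey's definition of opioids. The interventionist note that follows lists methadone and Suboxone as opioids.

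In eligibility (section 4.2), inclusion 2 asks for "Self-reported use of non-prescribed opioids in past 14 days" and inclusion 4 for "Urine positive for opioids by point-of-care testing during screening". The amendment of 08/06/2020 (Appendix 3) describes allowing "potential participants currently treated with methadone or buprenorphine for opioid use disorder" who report illicit use but "test negative for illicit opioids on urine drug screen to be enrolled if they test positive for cocaine or methamphetamine".

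**The concern.** Agonist treatment is both an opioid and a treatment for opioid use disorder. A participant who spends a full period on an agonist and uses no other opioid gains treatment days in 3b, yet could score every day or no day as abstinent in 3a. The same person could or could not count as abstinent in NOBWOS.

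The arms may well differ here. Methadone and buprenorphine are among the prevention strategies in the REBOOT session, and treatment options are discussed in the additional sections of the manual. Control content avoids drug use altogether. If REBOOT does raise agonist uptake, as 3b would allow, an unwritten rule decides whether those days help or hurt it in 3a. Aim 3 is listed as a primary objective, so the matter deserves a check.

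**Working it through.** The plan gives no rate, effect or power figure for Aim 3, so there is nothing of its own to reproduce. The stated power concerns overdose only. Every input below is assumed.

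**One participant.** Take a four-month period as 120 days. With 120 agonist days and no other opioid use, 3a is 120 if agonist days are not use, and 0 if they are.

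**Arm level.** Let B be the control mean of days free of non-prescribed opioids, and a the part of B spent on an agonist alone. Let x be the extra share of REBOOT participants on an agonist for m days with no other opioid use. Let p be the share of those m days that would have been opioid-free anyway.

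- Agonist days not scored as use: R1 = 1 + x·m·(1 − p)/B
- Agonist days scored as use: R2 = 1 − x·m·p/(B − a)

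Results:

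- B = 30, x = 0.10, m = 60, p = 0, a = 0: R1 = 36/30 = 1.20; R2 = 30/30 = 1.00.
- Smallest case over x of 5–15% and B of 20–60 days (m = 60, p = 0): x = 0.05, B = 60 gives R1 = 63/60 = 1.05.
- Largest case: x = 0.15, B = 20 gives R1 = 29/20 = 1.45. R2 stays at 1.00 throughout.
- First case with p = 0.5 and a = 10: R1 = 33/30 = 1.10; R2 = 17/20 = 0.85. The gap is 0.25 rather than 0.20, so it depends on p once controls also have agonist-only days. Randomization makes that likely if such people are enrolled.

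**Overlapping use.** A day with both an agonist and a non-prescribed opioid is a use day under either rule. If a share u of agonist days is of this kind, m becomes m(1 − u). In the first case, u = 0.5 gives 33/30 = 1.10 against 1.00, and u = 1 gives 1.00 against 1.00.

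**A second layout.** Suppose people off an agonist have 20 abstinent days, and people on one have 40 to 90 days free of non-prescribed opioids.

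| On agonist, control vs REBOOT | Only non-prescribed use counts | Any opioid counts |
|---|---|---|
| 10% vs 15% | 23/22 = 1.05 to 30.5/27 = 1.13 | 17/18 = 0.94 |
| 10% vs 20% | 24/22 = 1.09 to 34/27 = 1.26 | 16/18 = 0.89 |
| 30% vs 45% | 29/26 = 1.12 to 51.5/41 = 1.26 | 11/14 = 0.79 |
| 20% vs 20% | 1.00 | 1.00 |

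The direction can therefore reverse, but only if uptake differs by arm and the agonist days are largely free of other opioid use.

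**What the text supports.** The manual indicates that the survey's notion of an opioid includes agonists. It lists drugs; it does not classify days, and the outcome text does not refer to it. Read literally, it would make agonist days use days in 3a while the same days could count as treatment in 3b. Eligibility does not help: inclusion 2 is a self-report and inclusion 4 a urine test, each serving entry to the trial, and neither defines an outcome.

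**The case for a change.** The best case for a change is that two competent analysts could score 3a differently and each point to supporting text: the manual for counting agonist days as use, and the non-prescribed wording of inclusion 2 for not counting them. A choice made after results by arm are known would be open to suspicion. Settling it would take a sentence or a citation, and Aim 3 is a primary objective.

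It stands that the plan is silent, and that the answer could matter. But the silence does not show a wrong method. Nothing says that agonist days are scored in a way that conflicts with the aim, and no better analysis is being set against the planned one. The remedy would only write down what the survey already fixes, or what its analysts must decide in order to build the variable at all. A second coding as a sensitivity analysis would need prescribed status recorded by day, which the documents do not confirm. The contrast between arms is also softer than it looks, since section 1.2 offers treatment referrals on request to all participants.

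Two neighboring points do not alter this. The narrower treatment wording in the 8.4.1 heading, against the wider wording below it and in the objectives, is a minor slip for the sponsor to align. The synopsis and section 4.3 disagree on exclusion 2 when urine cannot be collected. Those passages must be reconciled, but that is a separate eligibility matter.

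**Conclusion.** The plan neither states nor cites how days on prescribed opioids count in outcome 3a or NOBWOS. That is a gap in detail which analysts using the survey would be expected to fill sensibly, and no change to the plan follows. On assumed inputs the coding moves the 3a ratio between 1.00 and 1.05–1.45, and in less favorable settings across 1 (for example 1.09–1.26 against 0.89). With equal uptake the computed ratios are both 1.00, and the gap shrinks towards zero as other opioid use occurs on the same days. The documents give no figures from which the true size could be derived.

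The conclusion rests on two assumptions: that the survey, which is not reproduced in the documents, holds enough to code these days, and that one coding is applied to both arms. The overdose analyses under Aim 2, the outcome that section 6.1 calls primary, and the sample size do not depend on it.
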